7 DISCONTINUATION OF TRIAL INTERVENTION AND PARTICIPANT WITHDRAWAL FROM TRIAL

7.1 Discontinuation of Trial Intervention

7.1.1 Criteria for Permanent Discontinuation of Trial Intervention

This is an orthopedic trial. The surgery is the start point and after the surgery there is no further treatment. There are only follow-up visits, which include an MRI (after 6 weeks, 6, 12, 24 months and 5 years in the operated group and after 24 months and 5 years in the non-operated group) and 3 questionnaires (IKDC and KOOS, CRF).

Criteria for permanent discontinuation for **single patients** from the trial are the following:

- Withdrawal of the informed consent
- lost to follow-up,
- premature death
- progression of osteoarthritis up to TKA
- the patient wishes to change to the operated group after a certain time

When withdrawal of the informed consent, premature death or lost to follow-up occurs, data up to the point will be used. If progression of osteoarthritis up to TKA occurs, the treatment is counted as treatment failure. These patients cannot continue the trial. Data up to the point will be used.

If the patient changes his decision and want to be operated at a later time point, the patient can continue the trial, but will be allocated to the other study arm. Data collected up to this point will be used in the first treatment group and then data will be generated in the second treatment group.

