8.1 Screening/Baseline Assessments and Procedures

The recruitment of patients for the investigator-initiated trial takes place during the consultation hours of the study centre. Since patients are specifically assigned for partial meniscus implantation, patients are already informed about the investigator-initiated trial at the time of appointment.

During the first visit (Screening) an MRI is done and evaluated, the inclusion and exclusion criteria are verified. If the patient qualifies for participation in the study based on the inclusion and exclusion criteria, he/she will be informed about the therapeutic procedure of partial meniscus implantation with Spongioflex® and the planned investigator-initiated trial (planned visits, data protection, etc.) will be explained. Patients also receive an information sheet explaining the surgical procedure, the advantages and disadvantages, the risks, and the follow-up treatment. After a sufficient reflection period, the patient must sign the informed consent form for participation in the investigator-initiated trial and the data protection declaration. Without these written consents, inclusion in the investigator-initiated trial cannot take place. After the signatures, the patient is included in the investigator-initiated trial. At this time point the patient must decide if he wants to be operated or not. In accordance with standard clinical practice, the usual risk information for the surgical procedure is provided for patients who decided to be operated. This is conducted based on the information sheet customary in the respective hospital. In this form, patients are usually informed about the procedure, the treatment alternatives, the risks, and the aftercare. Women are treated in the same way. Spongioflex® does not affect the body's metabolism and does not influence the effect of medications the patient is taking, thus there is no need for special female treatment options. There is no restriction for medication taken by the patient. For the control group (not operated patients) the follow-up visits are explained.

- Pregnant women are excluded from surgery
- Minor patients are not included

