9.1 Analysis Sets

Full analysis set will be performed.

PROMs:

Change from baseline for the PROMs (IKDC, KOOS, VAS-pain score) for the operated/non-operated group after 6, 12 and 24 months and 5 years and between groups.

Complications, AE, SAE and SUSARs:

The number of complications, AE, SAE and SUSARs will be evaluated at each time point and compared between the groups with Fishers exact test.

MRI evaluation:

Change in MRI evaluated using the Outerbridge [1] graduation, the size of the meniscal defect and the meniscus itself, the MRI signal of the meniscus will be evaluated after a modified score after Genovese et al.[32] and the number of patients with an extrusion and the size of the extrusion.

Patient satisfaction:

Patient satisfaction will be categorized as: very pleased, pleased, not pleased, very unsatisfied and will be evaluated using the Chi-square test.

Progression of osteoarthritis up to TKA:

The number of patients with progression of osteoarthritis up to TKA for both groups will be compared with a Kaplan-Meier time to event curve.

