9.3 Analysis Supporting Secondary Objective(s)

Secondary objectives are:

Safety of the patient, efficacy of the procedure, MRI image description and patient satisfaction.

Patient safety will be analyzing the number of AE, SAE and SUSARs and will be compared for both groups. The numbers obtained will be compared in a Chi-Square test. SUSARs will only occur, if any, in the operated group and thus cannot be compared to any other value. For categorial variables. Efficacy of the procedure will be analyzed by counting the number of failed procedures in the operated group. Because this value will only be determined in the operated group, there is no statistical analysis. The efficacy of the procedure must be over 80%. If the failed procedures are higher than 20 % the benefit-risk balance will be re-evaluated. The MRI signal will be evaluated after a modified scheme of Genovese [32]. The size of the meniscus and the amount of extrusion of the meniscus will be measured and recorded in both groups. The obtained numbers will be compared to the other group at the same time point and to the value before surgery/at the beginning of the trial. This will be performed with an unpaired t-Test if the values are normally distributed or with the Mann-Whitney-U-test for not normally distributed values. Patient satisfaction is a categorial value and will be only evaluated in the operated group. The number of patients who are very pleased, pleased, not pleased, very unsatisfied will be described by means of frequency tables and plots.

Intercurrent event are: progression of osteoarthritis up to TKA, lost to follow-up, premature death, the patient wishes to change to the operated group after a certain time. If these events happen, the data will be available until the event. Last date recorded will be analyzed. Progression of osteoarthritis up to TKA will be recorded as fail and will be reported as this. Patients changing to the operated group will be analyzed up to the date of change in the non-operated group. Missing data will not be estimated. A drop-out rate (lost to follow-up, premature death) of 20% is expected and accepted.

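### Section 9.3 applies unpaired tests to the comparison of meniscus size and extrusion with each patient's own baseline, which is a paired comparison

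*Protocol*

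**What the plan says.** Section 9.3 covers the MRI part of the secondary objectives. It states: "The size of the meniscus and the amount of extrusion of the meniscus will be measured and recorded in both groups". It then says that the numbers obtained "will be compared to the other group at the same time point and to the value before surgery/at the beginning of the trial". The sentence that follows is the only one on method: "This will be performed with an unpaired t-Test if the values are normally distributed or with the Mann-Whitney-U-test", the latter when normality does not hold.

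The baseline value comes from the same patients. Section 8.1 says: "During the first visit (Screening) an MRI is done and evaluated". Section 7.1.1 places follow-up MRI at 6 weeks, 6, 12 and 24 months and 5 years in the operated group, and "after 24 months and 5 years in the non-operated group". Section 9.1 also lists a change measure: "Change in MRI evaluated using the Outerbridge [1] graduation, the size of the meniscal defect and the meniscus itself".

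The t-tests named in sections 9.2, 9.2.1, 9.3 and 9.8 are all independent-group or unpaired tests. No paired t-test, signed-rank test or other within-patient method appears in the protocol.

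**The concern.** The unpaired t-test and the Mann-Whitney test both assume two independent samples. That holds for operated against non-operated patients. It fails for a patient's follow-up MRI against that patient's screening MRI.

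With positive within-patient correlation, the unpaired test attributes stable differences between patients to noise in the change. Its false-positive rate then falls below the nominal 5% and power is lost. A real change in meniscus size or extrusion, in either arm, could be reported as not significant. There is no single direction of bias in favour of one arm.

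MRI evaluation is a named secondary objective, and section 2.1 treats MRI as important and sensitive for judging meniscus function after surgery. Sections 4.1 and 10.4 have the investigator run the analysis himself, with a statistician only if needed, so the written rule may well be followed literally.

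**Working it through.** **The plan's own figures.** Section 9.8 gives power only for the patient-reported scores. For 10 against 30 patients, effect size d = 2.0 and α = 0.00655 two-sided, the noncentrality is 2.0 × √(10 × 30 / 40) = 5.48 on 38 degrees of freedom. Power is 0.9935 (stated: 0.993). For 8 against 24 at α = 0.014 it is 0.9857 (stated: 0.985). Both reproduce. They concern the between-group comparison of scores and do not bear on this point. No power is stated for MRI.

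**Inputs.** Group sizes are 30 and 10, or 24 and 8 after 20% loss (section 9.8). The two-sided 5% level is stated for the scores (sections 9.2 and 9.2.1) and assumed here for MRI. The SD σ, within-patient correlation ρ and true change δ for MRI are not given, so they are assumed and varied.

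**Why the unpaired test goes wrong.** With equal SDs, the variance of the mean within-patient change is 2σ²(1 − ρ)/n. The unpaired test estimates it as 2σ²/n, too large by a factor 1/(1 − ρ): 1.43 at ρ = 0.3, 2 at 0.5 and 3.33 at 0.7.

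**Paired power in closed form.** The noncentrality is δ√n / (σ√(2(1 − ρ))). For δ = 0.5σ, ρ = 0.5 and n = 30 it is 0.5 × √30 / 1 = 2.74. The critical t on 29 degrees of freedom is 2.045, which gives power 0.754.

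**Simulation.** Baseline and follow-up values were drawn as bivariate-normal pairs and tested both ways. Power for a 0.5 SD change with equal SDs, unpaired / paired:

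| n | ρ = 0 | ρ = 0.3 | ρ = 0.5 | ρ = 0.7 |
|---|---|---|---|---|
| 30 | 0.48 / 0.47 | 0.48 / 0.61 | 0.47 / 0.75 | 0.47 / 0.93 |
| 24 | 0.40 / 0.38 | 0.38 / 0.51 | 0.36 / 0.65 | 0.33 / 0.86 |
| 10 | 0.18 / 0.17 | 0.15 / 0.22 | 0.12 / 0.29 | 0.09 / 0.45 |
| 8 | 0.15 / 0.14 | 0.12 / 0.18 | 0.09 / 0.23 | 0.07 / 0.35 |

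With no true change and n = 30, the unpaired test rejects in 2.0%, 0.7% and 0.1% of runs at ρ = 0.3, 0.5 and 0.7. The paired test stays at about 5%.

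**Other settings.**
- Weak correlation (ρ = 0.1, n = 30): 0.48 against 0.51.
- Follow-up SD 1.5 times baseline (ρ = 0.5, n = 30): 0.27 against 0.52.
- Change of 1.0 SD, ρ = 0.5: 0.99 against 1.00 (n = 30), 0.59 against 0.80 (n = 10), 0.46 against 0.68 (n = 8).

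**Number of tests affected.** On the schedule in section 7.1.1, if every follow-up MRI is tested: 2 measures × (5 operated + 2 non-operated visits) = 14. Table 1 in section 6.1, read literally, puts MRI at every follow-up visit, which would give 2 × (6 + 4) = 20. Sections 7.1.2 and 9 support the smaller count.

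**The case against.** The strongest counter-argument is that section 9.3 is compressed and really means change from baseline compared between groups. Section 9.2.1 does this for the patient-reported scores, section 9.1 speaks of change in MRI, and the endpoint row in section 3.2 ends with the between-group comparison. An unpaired test on change scores would be correct.

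The text of 9.3 does not support this reading. It compares the values themselves with baseline, as a second item beside the between-group comparison. On the schedule in sections 3.2 and 7.1.1, the MRIs at 6 weeks, 6 months and 12 months exist for operated patients only. At those visits there is no control value, so comparison with baseline is the only one of the two that can be made, and it is within-patient. If the method sentence were meant for the between-group comparison alone, the baseline comparison would have no test and the same sentence would still need correcting.

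Three limits do stand.
- The consequence is modest: two measures under one of four secondary objectives, with no stopping or re-evaluation rule attached to them.
- The loss depends wholly on an unstated correlation. In the operated arm, ρ may be low or the SDs unequal, because the implant itself alters meniscus size.
- The error is conservative only if the correlation is positive. At ρ = −0.2 and n = 30, the unpaired t-test rejects in about 7.4% of runs when nothing has changed. A negative correlation is not the expected case, but the paired test holds its level there too.

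**Conclusion.** The point holds: the test that section 9.3 assigns to the comparison with own baseline is wrong as written, not merely left open. It should be fixed, but it does not threaten the trial's main conclusion.

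Under positive correlation the error costs power and does not add false positives. The cost runs from nothing at ρ = 0 to a power of 0.47 instead of 0.93 at ρ = 0.7 (n = 30, 0.5 SD change). A large change in the operated arm would be found either way. The non-operated arm still loses appreciably at a 1.0 SD change, although for a 0.5 SD change even the paired test has little power with 8 to 10 patients.

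These figures assume normal data, a two-sided 5% level and the stated values of ρ, SD and change, none of which the protocol supplies for MRI. They were computed for the t-tests; the Mann-Whitney test makes the same independence assumption. That the stated test does not fit the comparison depends on none of these values. The analyses of patient-reported scores are outside this point.

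**What to change.** Split the method sentence in section 9.3 in two:

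- For meniscus size and extrusion against the patient's own baseline, use the paired t-test on within-patient differences, or the Wilcoxon signed-rank test if those differences are not normally distributed.
- For operated against non-operated patients at the same visit, keep the unpaired t-test or the Mann-Whitney test.

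The normality check for the first comparison should be made on the differences, not on the raw values. The cost is one reworded sentence. No new data, visits or patients are needed.

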9.4 Analysis of Exploratory Objective(s)

Exploratory Estimand (Variable): Progression of osteoarthritis up to TKA.

The number of patients with progressing osteoarthritis up to TKA will be represented in a Kaplan-Meier-survival curve for both groups. The equality of the curves will be assessed using logrank tests.

9.5 Safety Analyses

Patient safety will be analyzed by recording AE, SAE and SUSARs. The number of these events will be recorded and compared for both groups. SUSARs will only occur, if any, in the operated group. The frequencies obtained will be displayed in bar plots and tables with group comparisons based on Fisher's exact test. Safety is a secondary outcome and is described in detail in 9.3.

9.6 Other Analyses

The KOOS score has sub-scores: symptoms, pain, activity in daily live, sport and leisure, and quality of live. These sub-scores will be analyzed in detail for the 2 groups. There will be no adjusted analysis.

9.7 Interim Analyses

Interim analysis will be performed 2 years after surgery/start of the trial. After knee surgery, the usual follow up is 2 years. Because long term results are important for the efficacy of the procedure, evaluations will be performed also after 5 years. The analysis will be performed by the investigator. The statistical methods used are described under 9.2 and 9.3. The outcome data will be seen only by the investigator while the trial is ongoing. The 2-years result will be published in an international orthopedic journal. There will be no group sequential test and no spending function. The number of patients is fixed at 30 in the operated group and at 10 in the non-operated group. There will be no enrollment until an event occurs. There will be no trial adaptation or changes to the eligibility criteria.

Stopping criteria are: If AE, SAE and SUSARs change the benefit-risk balance, there will be a new benefit-risk balance evaluation and after this evaluation it will be decided if the trial will be stopped. The investigator expects a maximal 20% failure rate of the procedure. If the failure rate is higher a new benefit-risk balance evaluation must be performed and after the evaluation it must be decided if the trial continues. If the safety of the patients is not any more given, the trial should be stopped.

The investigator also has the right to stop the trial. This could be because of the closure of the site. See 10.5 for details.

9.8 Sample Size Determination

The unpaired t-Test will be used for normally distributed PROMs. Values for the primary outcome are expected to be about 55/84 for the IKDC score and 46/86 for the KOOS pre/postsurgery, respectively. For this calculation, the program G-power was used. A sample size of 9 in the operated group and 3 in the non-operated group would be sufficient to reach a power of 0.982. When we include 10 non-operated patients and 30 operated patients the effect size is 2.0, $\alpha = 0.00655$ and the power is than 0.993. If we have a 20% lost to follow-up, the numbers of patients will be 8/24 and $\alpha = 0.014$ and the power will be 0.985. The number of 30/10 is sufficient to reach a power of >0.8.

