9.2.1 Statistical Model, Hypothesis, and Method of Analysis

The change in PROMS from baseline in the operated and non-operated group will be compared by two-sided t-test for independent groups when data are normally distributed or with the Mann-Whitney-U-test.

The Null-hypothesis is that partial meniscal replacement does not improve mean PROMs for knee function in comparison to the non-operated group after 2 and 5 years.

The alternative hypothesis is that there that partial meniscal replacement does improve mean PROMs for knee function in comparison to the non-operated group after 2 and 5 years.

The PROMS should improve (Mean KOOS and IKDC should increase by at least 20 points, and VAS-pain score should decrease by at least 3 points, or to near zero, depending on the pre-surgical value).

Analysis of data will be performed by direct comparison of the groups at each time point and in comparison, to before surgery/start of the trial. Mean and standard deviation of the groups are compared. If there is a significant difference, the Null-Hypothesis will be rejected. Even when we have a loss of follow-up of 20% the power will still be 0.985. From our experience mean KOOS values presurgical are between 40-50 and between 50-60 for the IKDC, after treatment the expected improvement is to mean values between 80-90 for both scores. For the VAS-pain-score the presurgical mean value is around 4 and the post-surgical value is between 0 and 1. There is no risk of a type 1 error, because the values are measured several times over the follow-up period, thus there will be no false positive result. If the difference in the scores between pre- and post-surgery is lower than 18, the power is not big enough. Thus setting 20 as the difference for rejecting the Null-hypothesis is supported by enough power, even with only 8/24 patients in the respective group. The covariate could be smoking and sex. Smoking affects healing in general. It is not clear if there will be enough patients in each group to use these as confounders. Interactions will not be possible, because the treatment has no relation to any characteristic of the patient. There will be no adjustment made and no model fitting.

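### The 0.982 power for 9/3 does not follow from the stated effect size, the sample-size alphas are not the test level, and the 20-point power claim has no SD behind it

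*Protocol*

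**What the plan says.** Section 9.8 of the protocol makes three power statements:

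- For the smallest size: "A sample size of 9 in the operated group and 3 in the non-operated group would be sufficient to reach a power of 0.982". No effect size or alpha accompanies it.
- For the planned size: "When we include 10 non-operated patients and 30 operated patients the effect size is 2.0", with alpha 0.00655 and power 0.993.
- After dropout: "If we have a 20% lost to follow-up, the numbers of patients will be 8/24", with alpha 0.014 and power 0.985.

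It concludes: "The number of 30/10 is sufficient to reach a power of >0.8". The expected scores are pre/post values for surgery only: "Values for the primary outcome are expected to be about 55/84 for the IKDC score and 46/86 for the KOOS pre/postsurgery".

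Section 9.2 sets significance at p < 0.05. Section 9.2.1 plans a two-sided unpaired t-test on change from baseline, with Mann-Whitney if the data are not normal. It adds a required improvement, "Mean KOOS and IKDC should increase by at least 20 points", and a lower limit, "If the difference in the scores between pre- and post-surgery is lower than 18, the power is not big enough". From this it concludes that 20 points is adequately powered even at 8/24, and it describes 20 as the threshold for rejecting the null. The same section also says: "If there is a significant difference, the Null-Hypothesis will be rejected".

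The protocol gives no SD for any score or its change. The expected change without surgery appears only in words, in section 2.2, as very unlikely to be an improvement.

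**The concern.** Sections 9.8 and 9.2.1 are the protocol's only justification of the sample size and of the 20-point figure. Five things do not fit together.

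1. The 9/3 power has no inputs of its own and looks too high for the one effect size stated.
2. The alphas in 9.8 differ from the test level in 9.2 and change with the number of patients.
3. The 20-point claim cannot be checked without an SD and a control change, and d = 2.0 is not tied to any score.
4. The 18-point limit is a pre/post difference with no stated power threshold, and 20 points also appears as an increase from baseline. The planned test compares change between groups.
5. A 20-point threshold and p < 0.05 are two different rejection rules.

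At stake is whether a reader can trust the stated power after dropout, and how a significant result below 20 points would be read.

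**Working it through.** **Method.** Exact power of the two-sample t-test from the noncentral t distribution: df = n1 + n2 − 2 and ncp = d × √(n1·n2/(n1 + n2)). Two-sided unless stated.

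**Inputs from the protocol.** d = 2.0, the sizes 9/3, 30/10 and 24/8, and alphas 0.00655 and 0.014 (9.8); two-sided test (9.2.1); 0.05 (9.2). Expected gains with surgery: IKDC 84 − 55 = 29, KOOS 86 − 46 = 40 (9.8).

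**Step 1: the plan's figures at d = 2.0.**

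| Operated/non-operated | ncp | df | Stated alpha | Stated power | Power at stated alpha | Power at 0.05 |
|---|---|---|---|---|---|---|
| 30/10 | 2.0 × √7.5 = 5.48 | 38 | 0.00655 | 0.993 | 0.9935 | 0.9996 |
| 24/8 | 2.0 × √6 = 4.90 | 30 | 0.014 | 0.985 | 0.9857 | 0.9973 |
| 9/3 | 2.0 × √2.25 = 3.00 | 10 | none | 0.982 | – | 0.771 |

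The first two rows reproduce. Solving for two-sided alpha = beta at d = 2.0 gives 0.0065 (30/10) and 0.0142 (24/8), so the printed alphas look like the output of such a calculation and not a chosen test level.

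The third row does not reproduce. Other variants at d = 2.0 also fall short: one-sided 0.05 gives 0.874, Mann-Whitney 0.747, the two-sided normal approximation 0.851, alpha = beta 0.888, and an equal 6/6 split 0.876. Power of 0.982 at 9/3 needs d = 3.02 at two-sided 0.05, or a two-sided alpha of about 0.40 at d = 2.0.

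**Step 2: power for 20 points.** The SD of change is not stated, so it is an assumption here. If d = 2.0 stands for 20, 29 or 40 points with no control change, the SD is 20/2 = 10, 29/2 = 14.5 or 40/2 = 20. For a true between-group difference of 20 points at two-sided 0.05:

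| Assumed SD | d = 20/SD | Power at 24/8 | Power at 30/10 |
|---|---|---|---|
| 10 | 2.00 | 0.997 | 0.9996 |
| 14.5 | 1.38 | 0.905 | 0.957 |
| 20 | 1.00 | 0.659 | 0.761 |

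Power of 0.80 needs d = 1.182 at 24/8 and 1.050 at 30/10. The largest SD that still gives 0.80 at 20 points is therefore 20/1.182 = 16.9 at 24/8 and 20/1.050 = 19.0 at 30/10. Improvement in the non-operated group would shrink the between-group difference and lower power.

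**Step 3: the two rejection rules.** The smallest observed difference with p < 0.05 is t(0.975, df) × SD × √(1/n1 + 1/n2). At 24/8, √(1/24 + 1/8) = 0.408 and t(0.975, 30) = 2.042, so the multiplier of the SD is 0.834. For SD 10, 14.5 and 20 this gives 8.3, 12.1 and 16.7 points. At 30/10 the values are 7.4, 10.7 and 14.8. In every case a difference well below 20 is already significant.

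**The case against.** The strongest reply is that d = 2.0 is attached to 30/10 and not to the 9/3 sentence. Since 9.8 lists two expected gains, the 9/3 figure may rest on another effect size, near 3, so this would be an omitted input and not an arithmetic error. That is possible, and the charge here is only that 0.982 cannot be reproduced from what is stated. The sentence still suggests a margin that the one stated effect size does not provide.

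Second, the alpha mismatch does no harm, because at 0.05 the powers are higher. This is accepted. It remains a contradiction with 9.2.

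Third, the unfavourable case needs SD 20. If the target of more than 0.8 is applied to the 18-point limit at 24/8, the implied SD is about 15.2, and 20 points would then have power of about 0.88. This is a reasonable inference, but the protocol states no threshold for the 18 points, so it cannot settle the matter. Failure of the 20-point claim is not shown; its dependence on an unstated SD is.

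Fourth, with no control change a pre/post gain equals the between-group difference in change, and the rule based on significance may be the operative one. Both readings are plausible, but the first needs a control change of zero to be stated and the second leaves a competing rule in the text.

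Finally, the sample size does not change. That is correct and limits the weight of the point.

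**Conclusion.** The concern holds.

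- The 0.982 for 9/3 does not follow from the stated inputs: 0.77 at the only stated effect size and the planned test.
- The alphas 0.00655 and 0.014 contradict the 0.05 level; the error is conservative.
- The claim of enough power for 20 points at 8/24 is unsupported as written. It meets the target of more than 0.8 if the SD of change is at most about 16.9. It does so if d = 2.0 stands for 20 points or for the 29-point IKDC gain, and misses (0.66) if it stands for the 40-point KOOS gain.
- Sections 9.8 and 9.2.1 mix pre/post with between-group differences and give two rules for rejecting the null.

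The SDs of 10, 14.5 and 20 are back-calculated assumptions with no control change. The planned 30/10 is not challenged: its claim of more than 0.8 holds for any d of about 1.05 or more.

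**What to change.** Keep 30/10.

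In section 9.8:

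- Delete the 9/3 sentence and the alphas 0.00655 and 0.014, and state two-sided alpha 0.05.
- Give the assumed between-group difference in change, the SD of change for each score with its source, and the assumed change in the non-operated group.
- Report power at 20 points over a stated SD range. For SD 10 to 20 it runs from above 0.99 to 0.76 at 30/10, and from 0.997 to 0.66 at 24/8. The sponsor's own sourced range should replace this one where available.

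In section 9.2.1:

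- Make the 20-point claim conditional on the SD (at most about 16.9 for 80% power at 8/24).
- State the power threshold behind the 18 points, and whether 18 and 20 are between-group or pre/post differences.
- Say that 20 is the assumed true difference used for power, and that the null is rejected on p < 0.05.

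The cost is text only, with no extra patients. The stated power at 20 points may become less favourable, depending on the SD and control change supplied.
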